- For Aim 1, to determine the target strain range, pilot subjects were classified as high and low responders (five and three subjects, respectively, based on observed 14 week changes in ultradistal BMC of $+2.57\%$ and $+0.51\%$). On average the high responders' peak Von Mises equivalent strains within the ultradistal volume were $3430\pm536\text{ }\mu\epsilon$, whereas the low responders' were $2125\pm432\text{ }\mu\epsilon$. Based on these results, we conclude strains below $1800\text{ }\mu\epsilon$ are unlikely to elicit a response, whereas we observed that strains above $3600\text{ }\mu\epsilon$ required forces in excess of 450 N for the average subject. Many women have difficulty applying this magnitude. Thus, targets of 1800 and $3600\text{ }\mu\epsilon$ were identified for this experiment.
- For Aim 2, the target strain magnitude, $3600\text{ }\mu\epsilon$, represents the largest strain magnitude that is achievable voluntarily by most female subjects. In our pilot subjects, this required a target force of $445\pm80\text{ N}$. Using the largest reasonable strain value maximizes the possible strain rate that is achieved with the impact loading group and maximizes the possibility that the loading elicits an osteogenic response. The strain rates that are assigned, $4500\text{ }\mu\epsilon$ and $36,000\text{ }\mu\epsilon$, respectively, are a function of the load application time generated with each of the two instruction sets. *The range of strain magnitudes produced using “slow” versus “impact” instruction sets represent nearly the entire range that can be voluntarily produced safely and consistently by subjects.*
- In both aims, subjects will apply 100 cycles of loading per day, 4 days per week, for 12 months. In our pilot subjects, this number of cycles per week was well tolerated by subjects and was osteogenic.

b. Sources of Materials

All research data will be obtained from the subjects specifically for research purposes.

- QCT data is uploaded to a secure cloud-based website (www.Lifelimage.com) for transfer to the laboratory. Per hospital procedure, all CT scans are read by a radiologist to ensure that no abnormalities are detected. Should the scan reveal abnormal pathology, the subject will be contacted directly by the radiologist. The CT scan is documented in each subject's medical record as a research CT scan.

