i. Radiation Dose: Each DXA scan exposes subjects to a total radiation dose of 0.05 mrem and subjects will receive one DXA scan each during screening. CT scans will result in an estimated radiation dose to subjects of 9 mrem per scan. HR-pQCT scans result in an effective radiation dose of 0.3 mrem per scan.

Subjects will receive 20.45 mrem (1 DXA plus 1 CT scan per arm x 2 arm x 9 mrem/scan plus 4 HR-pQCT scans/arm x 0.3 mrem/scan) over the first 12 month period, and 19.8 mrem (1 CT scan per arm x 2 arms + 3 HR-pQCT scans/arm x 2 arms) over the second 12 month period is expected.

ii. Mechanical Loading: Direct loading to the distal radius may cause some discomfort to subjects.

The alternative is to not participate in the research study.

2. Adequacy of Protection Against Risks

a. Recruitment and Informed Consent

Subjects will be recruited through physician referrals and by use of flyers, brochures, and word of mouth. Subjects will contact the Biomechanics Laboratory in response to either being directly asked to participate, or to seeing information about the study. If a subject appears to meet the study criteria, a letter of invitation will be sent to the potential subject and an appointment will be scheduled for them to speak with a member of the investigative team.

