Statistical Analysis Plan

A Prospective Study of Human Bone Adaptation Using a Novel in Vivo Loading Model

ID: 13-111

NCT #: not yet assigned

Originally created: 1/12/2012

Last updated: 1/12/2012 by [name]

Statistical Analysis Plan

Originally created: 1/12/2012

Last updated: 1/12/2012 by [name]

Statistics and Expected Outcomes:

An intent to treat analysis will not be employed here because the purpose of this research is to determine the link between *actual strains applied to bone* and the bone adaptive response. The present study is not intended to address the degree to which mechanical loading is an effective means to improve bone strength in a public health setting. Accordingly, adherence to the mechanical loading protocol is expected to influence the degree of adaptation and will be considered a potential explanatory variable for the following analyses.

For Experiment 1, hypotheses are related to the effect of strain magnitude.

For Experiment 2, hypotheses are related to the effect of strain rate. In both cases, the statistical analysis plan is the same, but tests will be performed on the corresponding variables (strain magnitude, or strain rate).

Hypothesis 1a: Bone mass will increase proportionally to the applied strain.

This hypothesis will be tested in two ways. In the first analysis, subjects will be analyzed by group (control, low, and high strain magnitude groups). For the group analysis, the 12-month change in whole radius total BMC will be analyzed as the primary dependent variable in a linear regression model with coefficients representing contrasts between each of the two experimental groups and the control group. Secondary outcome measures of trabecular BMC, ultra-distal BMC, fracture strength, moments of inertia, and others, will also be compared between groups using regression models for change scores at each of the four time points.

If our hypothesis is supported then there will be little change in the control group, a small but significantly higher increase in the 1800 $\mu\epsilon$ group, and a large and significantly higher increase in the 3600 $\mu\epsilon$ group. Similar models will be fit predicting change from baseline to 3, 6, and 9 months.

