In the second analysis, we will consider the *actual* strain magnitudes achieved by each subject, (which may differ from the group assigned strain), as a continuous variable, and will set the strain magnitude for control subjects to zero. The underlying assumption in doing this is that the baseline daily activity for *all* subjects is approximately equal, and is sufficient to maintain bone homeostasis. For this analysis, all four time points will be combined into a single model to examine changes across time after the loading regime has ended, and to compare the levels of applied strain. The dependent variable is the change score (in whole radius total BMC) from baseline; the independent variables are level of strain, time (3, 6, 9, 12 months), and a random intercept term for each subject to handle collinearity within repeated measurements. As in the first analysis method, secondary outcome measures of regional BMC, fracture strength, and others, will be considered as well.

If our hypothesis is supported then strain magnitude will be a significant predictor of change in whole radius total BMC and other related variables.

Hypothesis 1b: High initial bone mass, physical activity levels, and grip strength will be associated with diminished adaptive response for a given strain magnitude.

To test this hypothesis, initial BMC, grip strength, and physical activity will be added as potential covariates for the statistical models described in Hypothesis 1a.

If our hypothesis is supported then we would expect to observe an inverse relationship (negative coefficient) between initial bone mass, physical activity, grip strength, and change in BMC per group or per unit applied strain.

Hypothesis 1c: Bone structural changes will include increases in cortical diameter and thickness, and increased trabecular bone mass near the endosteal surface.

To test this hypothesis, the following variables will be examined:

For cortical diameter and thickness: integral and cortical bone mass and bone volume, compressive and bending strength index, and cross-sectional moments of inertia (bending and torsional)

For trabecular bone: trabecular bone mass and volume, cross sectional trabecular moments of inertia

Using the methods described for testing hypothesis 1a, changes in each of the specific variables listed will be examined at each time point. Here, the primary interest is in which specific quantities show the largest strain-related change.

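### The SAP's combined model is said to look at change after loading ends, but its four time points all fall within or at the end of the 12-month loading period, and it has no strain-by-time term

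*SAP*

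**What the plan says.** SAP, Hypothesis 1a, second analysis: the four visits are pooled in one model "to examine changes across time after the loading regime has ended", and also to compare levels of applied strain. The outcome is change from baseline in whole radius total BMC. The terms are listed in full: "the independent variables are level of strain, time (3, 6, 9, 12 months), and a random intercept term for each subject". Strain is the value each woman actually achieved, with controls set to zero.

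Protocol, section 1a, Rationale for Doses, for both aims: "subjects will apply 100 cycles of loading per day, 4 days per week, for 12 months".

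SAP, Hypothesis 1a, first (group) analysis: "the 12-month change in whole radius total BMC will be analyzed as the primary dependent variable". For the earlier visits, "Similar models will be fit predicting change from baseline to 3, 6, and 9 months".

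Protocol, section 1c.i, Radiation Dose, has the only scan counts in either document. The first 12 months have one DXA, one CT per arm and four HR-pQCT scans per arm. A further one CT and three HR-pQCT scans per arm are listed, with a dose that "over the second 12 month period is expected". Neither document gives a visit schedule or says what the second-period scans are for.

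**The concern.** One of the model's two stated purposes is out of reach of the data it uses. Month 12 is the end of loading, so a model built on months 3 to 12 describes the response during loading and nothing after it. If the sentence stands, a strain coefficient from the loading year could be reported as a post-loading finding. If scans after month 12 are taken, any analysis of them would be post hoc.

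The model's structure adds a second limit. With strain and time as separate terms only, the effect of strain is forced to be the same at every visit. The model cannot show a gain that builds up, levels off or is lost, and adding later visits to it unchanged would not cure that.

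**Working it through.** **1. Reproduce the protocol's dose figures, to confirm the scan counts.** Doses per scan (Protocol 1c.i): DXA 0.05, CT 9, HR-pQCT 0.3 mrem.

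- First period: 0.05 + 1×2×9 + 4×2×0.3 = 0.05 + 18 + 2.4 = 20.45 mrem. This matches the stated total. Counting HR-pQCT in one arm only would give 0.05 + 18 + 1.2 = 19.25, so both arms are meant.
- Second period: 1×2×9 + 3×2×0.3 = 18 + 1.8 = 19.8 mrem. This also matches.

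The counts can be relied on as read.

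**2. Compare the modelled times with the loading period.** Loading covers months 0 to 12. The model's times are 3, 6, 9 and 12. Times later than month 12: 0 of 4.

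**3. Look for another analysis that covers the period after loading.** The group analysis uses months 3, 6, 9 and 12. Hypotheses 1b and 1c reuse the 1a models. Hypothesis 1d names no time point. No SAP analysis names a time after month 12.

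**4. Count scans against analyses.**

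- HR-pQCT occasions per arm: 4 + 3 = 7 planned. The SAP's occasions are baseline plus four visits = 5. Remainder: 7 − 5 = 2. This assumes HR-pQCT at all five occasions; if any of the five lacks it, the remainder is larger.
- Placing month 12: with baseline counted in the first period, a fifth HR-pQCT occasion there would give 0.05 + 18 + 5×2×0.3 = 21.05 mrem, not 20.45. Month 12 therefore probably falls in the second period.
- CT: a second CT per arm in the first period would give 0.05 + 2×2×9 + 2.4 = 38.45 mrem, against the 21 mrem maximum in Protocol section 2b. Only two CTs per arm are planned, one per period. Hypothesis 1d, which uses change in QCT voxel density, needs both.
- Dose of the two unassigned occasions: 2×2×0.3 = 1.2 mrem, or 1.2/19.8 = about 6% of the second-period total.

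**5. Write out the model.** For subject i at visit t, with strain S_i:

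change_it = β0 + β1·S_i + γ_t + b_i + error

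The expected difference between a woman at strain s and a control (S = 0) is β1·s at every t. To illustrate, suppose that the effect grows linearly to its month-12 value, each woman has one strain value and all visits are complete. Then β1 estimates the mean over visits, which is (3 + 6 + 9 + 12)/(4×12) = 30/48 = 62.5% of the month-12 effect. The linear shape is my assumption. The general point is that one coefficient stands for four possibly different effects.

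**The case against.** Several points can fairly be made for the plan.

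- **Second-period scans.** A reader might infer that all the scans in the second 12-month period go unanalysed. The documents do not support that. By the counts above, the CT and one HR-pQCT occasion are probably the month-12 assessment, which serves the primary analysis and Hypothesis 1d. This objection stands, and only about two HR-pQCT occasions per arm are left over.
- **Retention is not a hypothesis.** Hypotheses 1a to 1d all concern adaptation to strain. The protocol's remark in section 3 about lasting benefit says only that fracture risk may be lower for some time afterwards. It would be wrong to read it as a study objective that the SAP fails to answer. This stands too, and it is why a post-loading model should depend on whether such visits exist.
- **Time-specific effects appear elsewhere.** The group models are fitted at each of the four visits, so effects by visit are planned for assigned groups. That softens the interaction point but does not remove it: the pooled model is the one that uses achieved strain, and as specified it has no visit-specific strain effect.
- **The phrase may say when the analysis is run.** That reading is strained, because the words are attached to the changes being examined. If the phrase is a slip, or a mismatch between the 2012 SAP and the protocol last modified in 2017, it still needs correcting.

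**Conclusion.** The concern holds in this limited form. The combined model cannot examine change after loading, because 0 of its 4 time points come after month 12, and no other SAP analysis covers that period. Without a strain-by-time term it also cannot show how the strain effect changes during the loading year. About 2 of 7 HR-pQCT occasions per arm have no planned analysis. That figure assumes HR-pQCT at baseline and at months 3, 6, 9 and 12, and it is uncertain because there is no visit schedule and the SAP does not name the scanner behind whole radius total BMC.

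A reader might also infer that the main result is compromised. It is not: the primary 12-month group contrast does not depend on this model. The point should be corrected before analysis, as a stated purpose that the specified model cannot meet.

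**What to change.** 1. In the SAP, delete the post-loading phrase from the 3-to-12-month model and add a strain-by-time term, so that the effect of achieved strain is estimated at each visit.
2. State the scan schedule: which scanner is used at which month, and which scans, if any, come after month 12.
3. If there are scans after month 12, pre-specify a model that includes those visits, with a strain-by-time term or a strain-by-phase term (loading, post-loading), so that retention of the 12-month gain is estimated. If there are none, claim no conclusion about the period after loading.

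The cost is SAP wording, one added interaction term and, only if the visits exist, one further model. No new scans are needed. The post-loading model could rest on as few as two HR-pQCT occasions per arm, so its precision should be described modestly.

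### The achieved-strain model for Hypothesis 1a lists no strain-by-time term, so it gives one visit-averaged slope and not the 12-month or time-varying response per unit strain: a cheap improvement

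*SAP*

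**What the plan says.** The SAP tests Hypothesis 1a in two ways.

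- **By assigned group.** The primary analysis contrasts each loading group with control on 12-month change in whole radius total BMC. Similar models are fitted at 3, 6 and 9 months, and secondary outcomes "will also be compared between groups using regression models for change scores at each of the four time points".
- **By achieved strain.** Strain is continuous, with controls set to zero. The SAP says that "all four time points will be combined into a single model to examine changes across time after the loading regime has ended". A second stated purpose is a comparison between strain levels. The outcome is change from baseline, and "the independent variables are level of strain, time (3, 6, 9, 12 months), and a random intercept term for each subject". Support for the hypothesis means that "strain magnitude will be a significant predictor of change in whole radius total BMC and other related variables".

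Setting controls to zero rests on the assumption that everyone's ordinary activity is about equal and "is sufficient to maintain bone homeostasis". Hypothesis 1b adds covariates to the 1a models. For Experiment 2, "the statistical analysis plan is the same, but tests will be performed on the corresponding variables", so strain rate takes the place of strain magnitude. No strain-by-time term appears anywhere in the SAP.

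**The concern.** For a change-from-baseline outcome, an additive model in strain and time says two things. The difference per unit strain is the same at month 3 as at month 12. Controls and loaded women also share one time trend. The second sits badly with the SAP's own expectation: if controls stay level and loaded women gain bone over the year, the time trend must depend on strain. The random intercept moves a woman's level up or down and does not free the slope by visit. Nor would a woman-level adherence main effect.

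The SAP sets aside intention-to-treat because its purpose is to link strain actually applied to bone response. This is the one 1a model that uses achieved strain. What is at stake is information on how that link develops over time, and the risk that the single coefficient is read as the 12-month dose-response.

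**Working it through.** The plan gives no effect size, SD or time course for this model, so there is no figure of its own to reproduce. The check is of structure, with assumed time courses.

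**Inputs.** Visits at 3, 6, 9 and 12 months (SAP). 20 women per group (Protocol, Introduction). Targets of 0, 1800 and 3600 microstrain, scaled s = 0, 0.5, 1 (Experiment 1), and 0, 4500 and 36,000 microstrain/s, scaled s = 0, 0.125, 1 (Experiment 2) (Protocol, Group Assignment). Four-week build-up of force (Protocol, Protection Against Risk). True change = D × s × f(t), where D is the high-group effect at month 12 and f(12) = 1. Controls are truly flat.

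**Pooled slope, strain fixed per woman.** With complete data the additive model returns the plain mean of the four visit slopes, whatever the random-intercept variance. As a share of the 12-month slope:

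| Assumed accrual | Mean of f(3), f(6), f(9), f(12) | Share |
|---|---|---|
| Cumulative load with linear four-week ramp | (11 + 24 + 37 + 50)/(4 × 50) | 0.61 |
| Linear | (0.25 + 0.5 + 0.75 + 1)/4 | 0.625 |
| Square root of time | (0.5 + 0.707 + 0.866 + 1)/4 | 0.77 |
| Linear to a plateau at 6 months | (0.5 + 1 + 1 + 1)/4 | 0.875 |
| Complete by 3 months | (1 + 1 + 1 + 1)/4 | 1.0 |

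Slower early accrual would go lower: quadratic gives (0.0625 + 0.25 + 0.5625 + 1)/4 = 0.47. I leave it outside the range because it implies an implausible gain. The pilot's 14-week ultradistal changes average (5 × 2.57 + 3 × 0.51)/8 = 1.80%, and 1.80 × (52/14)² is about 24.8% at 12 months. This is one time point in eight women at another site, so it is indicative only and cannot choose among the other curves.

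**Shared time trend.** Fitted control change is mean(s) × (f(t) − mean f) × D. Under linear accrual:

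- Experiment 1: 0.5 × (0.25 − 0.625) = −0.19D at month 3, and 0.5 × (1 − 0.625) = +0.19D at month 12.
- Experiment 2: 0.375 × (0.25 − 0.625) = −0.14D at month 3, and +0.14D at month 12.

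The true value is zero throughout.

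**Strain updated by visit.** If strain is a running mean with the same ramp, s is multiplied by 11/13, 24/26, 37/39 and 50/52. The pooled slope then also depends on within-woman correlation. Generalised least squares, as a random intercept implies, gives about 0.70 (ramp, correlation 0.50) to 1.03 (complete by 3 months, correlation 0.50) over correlations of 0.50 to 0.69. At 0.9 the ramp and linear cases are both about 1.05. All these correlations are assumed.

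**Precision of a month-12 slope, if one is added.** Assume change scores have measurement SD 1, a shared baseline error, and between-woman SD k in 12-month change. Month-12 variance is k² + 2. The variance of the four-visit mean is 0.3906k² + 1.25. The average single-visit variance, which a random-intercept model uses, is 0.46875k² + 2.

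- Single-visit SE over pooled SE: √(2/1.25) = 1.26 at k = 0, and √(11/4.766) = 1.52 at k = 3.
- Random-intercept SE over true SE at month 12: √(2.117/2.25) = 0.97 at k = 0.5, and √(6.219/11) = 0.75 at k = 3.

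**The case against.** The strongest reply is that nothing the SAP commits to fails. Hypothesis 1a is about proportionality to strain, the criterion is that strain predicts change, and the pooled slope tests that validly. The SAP does not name a 12-month slope as this model's target, and no hypothesis says that response per unit strain varies with time. The per-visit group models already show contrasts over time. The model is described in a prose list that leaves open how time is coded and whether strain is updated, so part of this is under-specification. The wording of the aim is itself unclear, and a time main effect also describes change across time.

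Most of that stands, and it sets the weight of the point. It does not remove it: the group models use assigned group, not achieved strain, and a shared time trend says nothing about strain-related change.

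Three stronger readings are tempting and are not supported.

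- **That the achieved-strain test is invalid.** In simulations with no strain effect and women differing in rate of change, the pooled test rejected at about 5%. The understated month-12 SE above is a hazard of adding visit-specific slopes with a random intercept alone. It is not a defect of the model as listed.
- **That Hypothesis 1c inherits this model.** The SAP says that for 1c "changes in each of the specific variables listed will be examined at each time point", which the per-visit group models can supply. Reuse of the pooled model there is not established.
- **That the coefficient must understate the 12-month response.** If the effect is complete by 3 months and strain is fixed, the ratio is 1.0. With visit-updated strain it can slightly exceed 1.

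**Conclusion.** The point holds as a cheap improvement to a supporting analysis. As listed, the only 1a model of achieved strain yields a visit-averaged slope. That slope answers whether strain predicts change. It does not give the 12-month dose-response or show whether the response per unit strain builds, holds or levels off. The same applies where 1b adds covariates to it and where Experiment 2 substitutes strain rate.

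The pooled slope is 0.61 to 1.0 of the 12-month slope with strain fixed per woman, or about 0.70 to 1.03 if strain is updated by visit and correlation is 0.50 to 0.69. Both ranges rest on assumed time courses, achieved strain equal to target, complete visits and flat controls. The absence of the term is certain from the text. The size of its effect is not. The primary 12-month group contrast is untouched.

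**What to change.** - Add strain × time with time categorical. Report the strain slope with its interval at each visit, including month 12.
- Keep the visit-averaged slope as the overall test, so that the stated criterion gains no extra test.
- State whether achieved strain is one value per woman or updated by visit.
- For the visit-specific slopes, allow a random slope or an unstructured covariance, at least as a sensitivity analysis. If women differ in rate of change, a random intercept alone understated the month-12 SE by 3% to 25% under the assumptions above (k = 0.5 to 3).

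**Cost.** SAP wording and no new data. The interaction adds three terms on up to 60 × 4 = 240 rows per experiment. An unstructured covariance has 10 parameters, or a correlated random slope 4, in place of 2. There are more estimates to report for each outcome, and a single-visit slope has an SE about 1.26 to 1.52 times the pooled one.

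**Separate wording point, adding no weight to the above.** The SAP's aim refers to change after loading has ended. The Protocol (Rationale for Doses) has loading last 12 months, so on that schedule none of the four visits follows it. The Protocol (Potential Risks, Radiation Dose) also counts scans in a second 12-month period. These passages should be reconciled. If any analysed visits are post-loading, name them and analyse them as a separate phase.

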Volunteers will be recruited from the communities surrounding Worcester Polytechnic Institute (WPI) including announcements made electronically and in person by members of the research team. Flyers and pamphlets explaining the study will be placed in the community, and, with permission, in the waiting room of the Family Practice clinic at the University of Massachusetts Medical Center. We will work with the institutional review board at WPI to ensure that all subject recruitment materials are compliant.

Screening:

All subjects will be verbally screened for inclusion/exclusion criteria by a member of the research team prior to being invited for a screening visit. During the screening visit, the subject's height and weight will be recorded. Subjects will receive a DXA scan of their nondominant radius and only those with BMD that falls within the specified range for inclusion will participate. Subjects will then visit the Quest Diagnostics Collection Center. There, six ml blood will be drawn via standard veinpuncture and sent to a local diagnostic laboratory (Quest Diagnostics) for a full metabolic profile including measurement of TSH, estradiol levels and Vitamin D concentration (total and 25,OH D₂ and D₃). This data will be interpreted by Drs. [name] and [name]. Potential subjects who have abnormal data and do not qualify for participation will be contacted by [name], given a copy of their laboratory results, and advised to consult their primary care physician. [name] will provide each of these individuals with his own clinical interpretation of the data, so that they understand the importance of their results.

All potential subjects who qualify to participate based on their screening will be invited to participate in the study. A signature of the informed consent document is considered a subject's written affirmation that she fits the inclusion/exclusion criteria.

Group Assignment:

For each Aim, eligible subjects will be randomized to one of two loading groups: a low, or a high group (20 subjects each) by having subjects draw a sealed envelope containing the group assignment. An additional 20 subjects will be randomized to a control (observation only) group. It is not possible to blind subjects or all team members to group assignment due to the nature of the experiment (team members cannot be blinded because group assignments must be known to assign target forces). However, all data will be blinded for analysis.

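### With only a random intercept, the combined change-score model gives wrong standard errors for change over time, in both directions, if women respond at different rates

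*SAP*

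**What the plan says.** The SAP, Hypothesis 1a, second analysis, combines all four follow-up visits in one model. "The dependent variable is the change score (in whole radius total BMC) from baseline". Strain level and visit time enter as predictors, and within-woman dependence is left to "a random intercept term for each subject to handle collinearity within repeated measurements". The model is meant "to examine changes across time after the loading regime has ended, and to compare the levels of applied strain".

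Neither document mentions a random slope, another covariance structure or robust standard errors. The SAP does not say whether time is linear or a factor, and it writes no strain-by-time term. Secondary outcomes are to be handled in the same way, and Hypotheses 1b and 1c reuse the Hypothesis 1a methods.

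The Protocol, Group Assignment, gives each Aim "a low, or a high group (20 subjects each"), and "An additional 20 subjects will be randomized to a control (observation only) group". That makes 60 women per model.

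**The concern.** A random intercept implies that change has the same variance at months 3, 6, 9 and 12 and the same correlation between every pair of visits. Change from baseline starts at zero. If women gain at different rates, its spread grows with time, and a random-intercept model books that divergence as independent residual noise. Standard errors for change over time, which is one of the two stated uses of the model, are then wrong.

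The documents give reason to expect unequal response. The SAP's opening paragraph expects adherence to affect the degree of adaptation. Hypothesis 1b states that women with different baseline traits will respond differently to the same strain. More weakly, the Protocol's Rationale for Doses reports that "pilot subjects were classified as high and low responders". Because the structure is reused for other outcomes, a spurious time trend could recur across them.

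**Working it through.** **Inputs from the documents.** 60 women; visits at 3, 6, 9 and 12 months; random intercept only. The plan states no SD, alpha or power, so there is no figure of its own to reproduce.

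**Assumptions.** Two-sided 5% test; complete data; SD of true 12-month change 1-3%, so slope SD s = 0.083-0.25% per month; scan error SD e = 0.5-1%. The true change at month t is (woman's slope × t) + scan error − shared baseline error.

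**Formulas** (n women; squared deviations of the visit times from their mean of 7.5 sum to 45; mean t² = 67.5).
- Linear time: the model variance is (s²/3 + e²/45)/n; the true variance is (s² + e²/45)/n.
- Two visits d months apart: the model variance is 2(e² + 15s²)/n; the true variance is (d²s² + 2e²)/n.
- Strain effect at month t, if fitted: the model uses the pooled variance 67.5s² + 2e²; the true variance is t²s² + 2e².

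**Worked example: SD 2%, e = 1%, so s² = 1/36 = 0.0278.**
- Linear time: model 0.0093 + 0.0222 = 0.0315; true 0.0278 + 0.0222 = 0.0500. SE ratio √(0.0315/0.0500) = 0.79, so the test rejects with probability 2[1 − Φ(1.96 × 0.79)] = 12%.
- Month 12 versus 3: model 2.83, true 4.25, SE ratio 0.82.
- Adjacent visits: model 2.83, true 2.25, SE ratio 1.12.
- The change-score SD is √(0.25 + 2) = 1.5% at month 3 and √(4 + 2) = 2.4% at month 12.

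**Model SE divided by true SE, from the mildest to the strongest setting in the assumed range.**

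| Effect | SD 1%, e 1% | SD 2%, e 1% | SD 3%, e 0.5% |
|---|---|---|---|
| Linear time | 0.92 | 0.79 | 0.62 |
| – rejection at nominal 5% | 7% | 12% | 22% |
| Month 12 vs 3 | 0.93 | 0.82 | 0.65 |
| Visits 6 months apart | 0.99 | 0.97 | 0.93 |
| Adjacent visits | 1.03 | 1.12 | 1.50 |
| Strain effect, month 3 | 1.09 | 1.31 | 2.11 |
| Strain effect, month 6 | 1.05 | 1.14 | 1.31 |
| Strain effect, month 9 | 0.98 | 0.95 | 0.92 |
| Strain effect, month 12 | 0.91 | 0.80 | 0.70 |

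With s = 0 every ratio is 1.00: the shared baseline error is absorbed by the random intercept.

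**Check by simulation** (60 women, 4,000 runs per setting, slope SD 0.1, 0.2 and 0.3% per month in all women).
- The linear-time test rejected 8.4%, 13.7% and 17.8% at e = 1%, and 13.6%, 21.2% and 23.8% at e = 0.5%. The top slope SD, 0.3 × 12 = 3.6% over 12 months, lies beyond the range in the table.
- Analysing per-woman slopes, equivalent to a random slope in balanced data, gave 4.4-5.4% over all settings run.
- The strain main effect rejected 4.8-5.5% when all women's slopes varied, and 2.4-4.1% when only loaded women's slopes varied.

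**Pilot, for scale.** Five women at +2.57% and three at +0.51% give a between-class SD of (2.57 − 0.51) × √(15/64) = 2.06 × 0.484 = 1.0 point at 14 weeks.

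**What a richer covariance does to a lone strain main effect.** At SD 2%, e = 1%, generalised least squares weights the visits in proportion to 1 − 0.098t, which normalises to 0.67, 0.39, 0.11 and −0.17. The weighted mean time is 0.67×3 + 0.39×6 + 0.11×9 − 0.17×12 = 3.33 months (unrounded weights). A strain effect growing linearly with time would be estimated at 3.33/12 = 0.28 of its 12-month value. The random-intercept model weights visits equally and gives 7.5/12 = 0.62.

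**The case against.** The strongest reply is that no hypothesis decision is harmed. The SAP's success criterion for this model is that strain predicts change. That is a between-woman comparison and keeps its error rate with complete data. The primary group analysis uses one 12-month value per woman, as do the companion models at 3, 6 and 9 months. All of this stands, and it limits the point to inference on time.

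Three further objections also stand in part.
- A reader might infer that every time test, or every visit-specific strain effect, is too liberal. The plan does not fix the form of time, and with a factor the pooled variance makes adjacent-visit contrasts and early strain effects conservative. Nor does a strain-by-time error rate belong to the plan as written, because that term is absent.
- A reader might take the pilot as proof of fan-out. It is eight women at one time point, on ultradistal rather than whole-radius BMC, classed by their observed change. Scan error alone at the assumed 0.5-1% gives a change-score SD of 0.7-1.4% (√2 × e), which at the upper end covers the 1.0 point. The classes also differed in strain (3430 versus 2125 µε), which is the model's own covariate.
- The purpose clause speaks of the period after loading ends, whereas the Protocol has loading continue for 12 months, so the listed visits do not match it. Those passages need reconciling. The point does not depend on the outcome, because time over months 3-12 is an explicit term in the model.

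Adherence and the Hypothesis 1b traits are planned as explanatory terms, but entering them as main effects would not remove variation in slopes.

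**Conclusion.** The point holds as a specification fault in a secondary use of the model. If slopes differ between women, the linear-time SE is 0.62-0.92 of its true value (rejection 7-22% at nominal 5%), and the month 12 versus 3 SE is 0.65-0.93 of its true value. Adjacent-visit SEs are 1.03-1.50 times too large. Strain effects at months 3 and 6, if fitted, have SEs 1.05-2.11 times too large; at month 12 the SE is 0.70-0.91 of the true one.

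The direction follows from algebra. The size rests on assumed SDs that the documents do not give, and it vanishes if slopes do not vary. A reader might infer that the Hypothesis 1a test or the 12-month result is unsafe. The calculations do not support that: with complete data neither becomes anti-conservative. The effect of missing visits was not examined.

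**What to change.** In the SAP, second analysis under Hypothesis 1a:
- Fit visit as a four-level factor with a strain-by-visit term, an unstructured 4×4 covariance (10 parameters, 60 women) and Kenward-Roger degrees of freedom.
- Report the strain effect at 12 months and averaged over visits.
- If the model does not converge, fall back to a random intercept plus random slope, keeping the strain-by-time term.
- Do not change the covariance while keeping only a strain main effect, because that moves the weight to early visits and shrinks an effect that grows with time.

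The cost is a few sentences and a few more parameters in standard software, with no new data. Intervals widen for long-span time effects and for the 12-month strain effect: at SD 2% and error 1%, by about 1/0.79 = 1.27 for the linear trend and 1/0.80 = 1.25 for the 12-month strain effect. That widening is the correction itself.
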